Observational Study Information

Acronym/Title	Observational Studies in Cancer Associated Thrombosis for Rivaroxaban – United Kingdom Cohort (OSCAR—UK)
Protocol version and date	V1, 23 Aug 2021
IMPACT study number	22020
Study type / Study phase	Observational, Phase IV PASS: Yes Joint PASS:  YES  NO
EU PASS register number	Study not yet registered
Active substance	Direct factor XA inhibitor, Rivaroxaban (B01AF01) Direct acting Oral Anticoagulants (DOACs): factor Xa inhibitors: rivaroxaban, apixaban, edoxaban; factor IIa inhibitor: dabigatran
Medicinal product	BAY 59-7939; 1912, Rivaroxaban, Xarelto® Direct acting Oral Anticoagulants (DOACs): factor Xa inhibitors: rivaroxaban, apixaban, edoxaban; factor IIa inhibitor: dabigatran
Product reference	Not applicable
Procedure number	Not applicable
Comparator / Reference therapy	Low molecular weight heparin (LMWH): Dalteparin, Enoxaparin, Tinzaparin
Study Initiator and Funder	Bayer AG, 51368 Leverkusen
Research question and objectives	The objective of this study will be to evaluate the effectiveness (recurrent VTE) and safety (major bleeding and bleeding-related hospitalization) of rivaroxaban and other DOACs vs. LMWH for treatment of CAT in the UK CPRD dataset
Country(-ies) of study	UK
Author	PPD Guy's and St Thomas' Hospitals NHS Foundation Trust, King's College London, [name] PPD Bayer AG

ONS	Office of National Statistics
OS	Observational study
OSCAR—UK	Observational Studies in Cancer Associated Thrombosis for Rivaroxaban – United Kingdom
PASS	Post-authorization safety study
PCP	Primary care practitioner
PE	Pulmonary embolism
PY	Person-year
RCT	Randomized controlled trial
RDG	Research data governance process
RECORD-PE	Observational routinely collected health data statement for pharmacoepidemiology
VTE	Venous thromboembolism

3. Responsible parties

3.2 Collaborator(s)/External partner(s)/Committee(s)

Role: External Physician and Clinical Epidemiologist

Name: PPD [redacted]

LIRN Limited, [name]

Role: External Physician and Clinical Epidemiologist

Name: PPD

Institute for Epidemiology, Statistics and Informatics (IfESI), [name]

4. Abstract

Acronym/Title	Observational Studies in Cancer Associated Thrombosis for Rivaroxaban – United Kingdom Cohort (OSCAR—UK)
Protocol version and date	V1, 23 Aug 2021
IMPACT study number	22020
Study type / Study phase	Observational / Phase 4
Author	PPD [Redacted]
Rationale and background	
Patients with active cancer are ~5-fold more likely to develop a venous thromboembolism (VTE) than those without. When VTE occurs, cancer patients carry an up to a 3-fold higher rate of thrombosis recurrence and ~twice the risk of bleeding during anticoagulation. Therefore, it is critical to utilize anticoagulants that optimize efficacy while minimizing bleeding risk when treating cancer-associated thrombosis (CAT).
 
The strength-of-recommendation for DOACs is based on data from multiple randomized controlled trials (RCTs) comparing them to LMWHs to treat CAT, with results suggesting DOACs may reduce thrombosis risk but with potentially more frequent bleeding (particularly in those with gastrointestinal and genitourinary cancers).
 
Observational studies evaluating DOACs for CAT treatment have been published, but these studies have been either single-arm, evaluated cancer subtypes not recommended for DOAC treatment (e.g., gastrointestinal, genitourinary), were of limited sample size and/or employed heterogeneous definitions of active cancer.

Research question and objectives	The objective of this study will be to evaluate the effectiveness (recurrent VTE) and safety (major bleeding and bleeding-related

	hospitalization) of rivaroxaban and other DOACs vs. LMWH for treatment of CAT in the UK CPRD dataset.
Study design	Retrospective cohort study.

Guidelines list direct-acting oral anticoagulants (DOACs) as an alternative to low molecular-weight heparin (LMWH) for treatment of CAT. The strength-of-recommendation for DOACs is based on data from multiple randomized controlled trials (RCTs) comparing them to LMWHs to treat CAT, with results suggesting DOACs may reduce thrombosis risk but with potentially more frequent bleeding (particularly in those with certain gastrointestinal and genitourinary cancers).

Observational studies evaluating DOACs for CAT treatment have been published, but these studies have been either single-arm, evaluated cancer subtypes not recommended for DOAC treatment, were of limited sample size and/or employed heterogeneous definitions of active cancer. We sought to evaluate the effectiveness and safety of rivaroxaban versus LMWH for CAT treatment in active cancer patients using a large de-identified electronic health record database.

This study is part of the OSCAR study program with independent studies in the US, UK and Sweden. One aim of the program is to conduct a meta-analysis of the results of the three studies to increase the study size and power. Harmonization of the studies design and definitions was intended, and thus this protocol is based on the protocol developed by the study team for the OSCAR-US Study (impact number 21982).

8. Research questions and objectives

What is the comparative effectiveness and safety of rivaroxaban vs LMWH and of DOACs vs LMWH for CAT treatment in active cancer patients?

8.1 Objectives

The objective of this study will be to evaluate the effectiveness and safety of rivaroxaban versus LMWH and of DOACs (as a group) versus LMWH for CAT treatment in active cancer patients using the CPRD dataset, specifically:

- Compare effectiveness and safety (primary and secondary outcomes) of rivaroxaban versus LMWH prescribed for treatment of VTE, at 3, 6 and 12-months of treatment in patients with acute VTE and active cancer without a malignant neoplasm associated with a high risk of bleeding, defined per:
 - Section 6.1 of the Xarelto® SmPC (i.e. gastrointestinal and genitourinary cancers).
 - The International Society on Thrombosis and Haemostasis (ISTH) guidelines (i.e. gastric, esophageal, unresected colorectal, bladder, central nervous system, and hematological cancers (except for myeloma)) [3].

Primary outcomes:

- Risk of recurrent VTE (fatal and non-fatal).
- Any major bleeding or clinically relevant bleeding-related hospitalization.
- All-cause mortality.

Secondary outcomes:

- Intracranial hemorrhage (ICH), other critical organ bleeding and extracranial bleeding-related hospitalizations as separate outcomes.
 - Please refer to section 9.3.2 for detailed definitions of all secondary outcomes.
- Compare effectiveness and safety (primary outcomes) of all DOACs (as a group) vs LMWH in active CAT patients without a malignant neoplasm associated with a high risk of bleeding.
 - Estimate incidence rates of recurrent VTE, any clinically relevant bleeding-related hospitalization and all-cause mortality in patients with active CAT with DOAC and LMWH treatment in the overall CAT cohort, i.e. regardless of the bleeding risk associated with cancer type.

- Estimate duration of anticoagulation treatment and DOAC and LMWH discontinuation rates at 3-, 6- and 12-months and all available follow-up data.
- Conduct subgroup analyses on cancer specific populations (potential cancer types: breast, prostate, lung, ovarian, pancreatic, etc.).

9. Research methods

9.1 Study design

[figure not shown]
We will perform a retrospective cohort analysis using CPRD GOLD and Aurum HES-linked datasets, from January 2013 through latest available data. Patient identification and flow is depicted in **Figure 1**.

Adults diagnosed with active (primary or metastatic) cancer experiencing a hospitalization or emergency department admission or a primary care visit with an incident VTE, being administered rivaroxaban or other DOACs or a LMWH will be included. CPRD and their linked databases do not include information on in-hospital medication use. Patient discharge with anticoagulation supply is routine practice. However, neither the type of AC use, the date of medication start nor the amount of supply are recorded in CPRD or linked databases. Therefore, the first AC recording by the GP, between day 7 and day 30 after index date, will be used to define the type and duration of AC use and to allocate patients with acute VTE to the respective exposure, i.e. DOAC or LMWH. The 7-30 days window has been selected based on previous studies in this population [2, 4]. Subjects will need to be registered with their primary care practitioner (PCP) for at least 12-months prior to the acute CAT event.

Active cancer in this study will be defined as cancer being actively treated, diagnosed within 6-months prior of the index CAT or associated with metastatic disease (regardless of time from initial cancer diagnosis). We will exclude patients with an indication for OAC use to treat other conditions (i.e. atrial fibrillation, prophylaxis after hip/knee replacement in the last three months, stable coronary or peripheral artery disease, long-term VTE prophylaxis) or use of OAC during the 12-months prior to the CAT.

Figure 1: Schematic of VTE analysis

9.2 Setting

General Practice setting in the UK (CPRD GOLD and Aurum HES-linked databases). The CPRD databases contain longitudinal routinely-collected electronic health records (EHR data) from UK primary care practices. GP practices use two different software systems (in structure and clinical coding), and due to these differences, data are provided as two separate primary care databases that can be pooled (CPRD GOLD and Aurum) and general practices duplicated in GOLD and Aurum can be identified and removed accordingly. The databases (GOLD and Aurum) capture information on: demographic characteristics, diagnoses and symptoms, drug exposures, vaccination history, laboratory tests referrals to hospital and specialist care and can be linked to national secondary care databases like Hospital Episode Statistics (HES) as well as death registration data [5-7].

CPRD databases contain information of patients of all ages to provide a representative sample of UK patients with CAT.

9.2.1 Study population

The study population of interest will be adults diagnosed with active (primary or metastatic) cancer experiencing a hospitalization or emergency department admission or a primary care visit with an incident VTE, being administered rivaroxaban or other DOACs or a LMWH on or after January 1, 2013. We will identify the first record of anticoagulant therapy between day 7 and day 30 following CAT diagnosis. Subjects will need to be registered with their PCP for at least 12-months prior to the acute CAT event. Patients with cancer diagnoses and/or cancer-specific therapies including chemotherapy, radiotherapy, hormonal therapy and immunotherapy will be identified. Active cancer will be assumed to last 180 days following a cancer diagnosis or therapy recording. Active cancer episodes will be extended for 180 days from the day of the subsequent cancer-specific recording if it is recorded within the initial active cancer episode. Metastatic cancers will assumed to be active ever since first recording.

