9.3.3 Covariate definition

Patient baseline characteristics such as age, gender, comorbidities, cancer-specific data and comedications will be collected at the index date or from the last recorded value within the baseline period. The presence of characteristics will be assessed from patients' medical and pharmacy data in the baseline period (see Annex 1).

Demographic characteristics

- Sex
- Age
- Race
- Individual DOAC or LMWH used to treat CAT
- Number of days between CAT and first recording of anticoagulation use

Clinical characteristics

- Presence of the following clinical characteristics will be assessed from patients' medical and pharmacy data in the baseline period:
 - **Comorbidities/prior history/risk scores:**
 - Number of days from January 1, 2013 to qualifying CAT diagnosis
 - Cancer type(s) present at CAT diagnosis
 - Metastatic disease at time of CAT diagnosis
 - Active/recent treatment (within 3-months pre- or post-CAT diagnosis)
 - Chemotherapy/immunotherapy
 - Radiation therapy
 - Surgical
 - Initial anticoagulation therapy on day of CAT diagnosis
 - Intracranial bleeding
 - Systemic embolism
 - Deep vein thrombosis
 - Pulmonary embolism
 - Heart failure
 - Hypertension
 - Ischemic stroke/transient ischemic attack
 - Peripheral vascular disease
 - Myocardial infarction
 - Percutaneous coronary intervention
 - Coronary artery bypass grafting
 - Any major bleed

- Major adverse limb events (need for surgical or endovascular revascularization or limb amputation)
- Gastrointestinal bleeding
- Central venous catheter
- Liver disease
- Coagulopathy
- Gastroesophageal reflux disease/heartburn
- Anemia
- Asthma
- Chronic obstructive pulmonary disease
- Sleep apnea
- Smoker
- Alcohol abuse
- Anxiety
- Depression
- Lower extremity paralysis
- Psychosis
- Osteoarthritis
- Diverticulitis
- Crohn's disease or ulcerative colitis
- Active or treated *Helicobacter pylori*
- Hypothyroidism
- Recent major surgery within 12 weeks of index event
- Dementia
- Recent trauma (with 90-days)

- Primary hypercoagulable state (e.g., activated protein C resistance, prothrombin gene mutation, antiphospholipid syndrome, lupus anticoagulant syndrome and other primary thrombophilia (per Read code; ICD-9 or -10 coding provided in Annex 1))
- Prior history of VTE
- Varicose veins
- Chronic venous insufficiency (per Read code or ICD-9 /-10 coding provided in Annex 1)
- Acute coronary syndrome
- Carotid stenosis
- Pneumonia
- Osteoporosis
- Orthopedic surgery

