- Rheumatoid arthritis/collagen vascular disease
- Proteinuria
- Ischemic (coronary) heart disease
- Number of hospitalizations for any cause during the baseline period
- Vascular disease (defined as myocardial infarction, peripheral artery disease or aortic plaque)
- Frailty (per specific Frailty Score)
- **Comedications**
 - Aspirin
 - P2Y12 Inhibitors
 - Other antiplatelet agents
 - NSAIDs
 - COX-2-specific NSAIDs
 - ACE inhibitors or ARBs

- β -blockers
- Diltiazem
- Verapamil
- Dihydropyridine calcium channel blockers
- Loop diuretic
- Thiazide diuretic
- Digoxin
- Amiodarone
- Dronedarone
- Other antiarrhythmic drugs
- Statins
- Other cholesterol lowering drugs
- Metformin
- Sulfonylureas or glinides
- Thiazolidinediones
- Dipeptidyl peptidase-4 inhibitors
- Glucagon-like peptide-1 agonists
- Insulin
- Benzodiazepines
- SSRIs or SNRIs
- Other antidepressants
- Proton pump inhibitors
- Histamine-2 receptor antagonists
- Systemic corticosteroids
- Exogenous estrogen therapies

- Strong CYP3A4 inhibitors (e.g., protease inhibitors, -azole antifungals)
- Strong CYP3A4 inducers (e.g., phenytoin, carbamazepine, rifampin, St. John's wort)
- Chemotherapy agents (various)
- Laboratory values and vital signs at baseline
 - SBP
 - DBP
 - Hemoglobin
 - D-Dimer
 - Serum creatinine
 - Reported eGFR
 - Height
 - Weight
 - Body mass index (BMI)
 - Platelet count

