Propensity scores will be estimated based upon commonly used variables and accepted risk factors for differential anticoagulation exposure identified during the baseline period including demographics, comorbidities, laboratory and vital signs and concurrent outpatient co-medication use. All clinical characteristics listed in section 9.3.3 of this protocol will be included in the propensity score model. Given the retrospective nature of the data analysis, the presence of a comorbid disease diagnosis will be identified based upon the recording of the specific comorbid read codes. Missing data for covariates will occur when an existing co-morbidity or co-medication is not recorded in the database. In such case we will assume that the respective patient did not suffer from the respective co-morbidity/did not use the respective co-

Reference Number: RD-SOP-1214
Supplement Version: 7

medication. Information on time varying variables e.g. BMI and smoking status will assumed to be constant unless a different variable entry is recorded. Whenever meaningful, missing data will be presented in separate categories labelled "not stated" or "unknown". No imputation will be performed for potentially missing outcomes/endpoint data. Separate propensity score models will be fit once for the primary analysis and for each subgroup analysis.

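### Hormonal cancer therapy and recency of cancer diagnosis define active cancer but are missing from the propensity score, so balance on them is not assured

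*Protocol*

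**What the plan says.** **Who has active cancer.** Section 9.1 accepts a cancer under active treatment, or one that is "diagnosed within 6-months prior of the index CAT or associated with metastatic disease (regardless of time from initial cancer diagnosis". Section 9.2.1 makes this operational. Patients with cancer diagnoses and/or "cancer-specific therapies including chemotherapy, radiotherapy, hormonal therapy and immunotherapy will be identified", and "Active cancer will be assumed to last 180 days following a cancer diagnosis or therapy recording". A further cancer record inside an episode extends it by another 180 days. Metastatic cancer stays active from its first record.

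**What is adjusted for.** Section 9.3.3 lists cancer type, metastatic disease and "Active/recent treatment (within 3-months pre- or post-CAT diagnosis"). That last item has three parts: "Chemotherapy/immunotherapy", radiation therapy and surgery. The comedication list adds "Chemotherapy agents (various"). Section 9.7 says twice that all clinical characteristics in section 9.3.3 enter the propensity score.

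**What follows.** Section 9.7 claims balance for the variables in the score, concedes that weighting cannot adjust for characteristics outside it, and fits a Cox model with the anticoagulant as the only independent variable. A separate score is fitted for each subgroup.

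**Drug records.** Section 9.1 states that "CPRD and their linked databases do not include information on in-hospital medication use". Section 9.7 states that "Missing data for covariates will occur when an existing co-morbidity or co-medication is not recorded in the database", and then treats the patient as not having the condition or not using the drug.

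**The concern.** Eligibility brings together patients at quite different points in their disease. One may be weeks from diagnosis. Another may be years from diagnosis, with no metastases, and active only because repeat hormonal prescriptions keep renewing the 180-day period. These patients plausibly differ in their risk of death, recurrent thrombosis and bleeding, and plausibly also in whether an oral drug or injections are chosen. If so, both omitted items are confounders.

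The protocol has to derive the underlying information to decide eligibility, yet does not carry it into the adjustment set. At stake are the three primary comparisons at 3 months, all-cause mortality above all, and their repetition within cancer subtypes.

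**Working it through.** No figure in the protocol quantifies this point, so the check is first a comparison of lists and then an illustration on assumed values.

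**1. Eligibility items against covariates.**

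| Used to define active cancer (9.1, 9.2.1) | Term in 9.3.3? |
|---|---|
| Chemotherapy | Yes, within 3 months of the thrombosis |
| Immunotherapy | Yes, combined with chemotherapy |
| Radiotherapy | Yes, within 3 months |
| Hormonal therapy | No |
| Recency of cancer diagnosis | No |
| Metastatic disease | Yes |

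Three of the four therapy types have a term. Two other items look close but are not substitutes. The estrogen comedication item does not cover anti-cancer hormonal therapy as a class. The count of days from 1 January 2013 is calendar time, not time since cancer diagnosis.

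**2. The windows differ.** A therapy record confers active status for 180 days, but the treatment covariate looks back only 3 months. A patient who qualifies on chemotherapy given four months earlier can score no on every recent-treatment term, just like a hormonal-only patient.

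**3. Later steps do not repair the gap.** The outcome model has no covariates. The 1:1 matching sensitivity analysis is also based on propensity scores, and no other covariate set is stated for it.

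**4. Subtype analyses.** Section 8.1 names breast and prostate among the possible cancer types. Within one type the cancer-type term is constant and cannot stand in for hormonal therapy or time since diagnosis.

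**5. Illustration of size.** Let p1 and p0 be the weighted proportions with an omitted binary factor in the rivaroxaban and LMWH groups, and R its hazard ratio for the outcome. With no true drug effect, the observed hazard ratio is approximately

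B = [1 + p1(R − 1)] / [1 + p0(R − 1)].

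All values of p1, p0 and R are assumptions; the protocol gives none.

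| p1 | p0 | R | B |
|---|---|---|---|
| 0.20 | 0.10 | 0.3 | 0.86/0.93 = 0.925 |
| 0.20 | 0.10 | 0.5 | 0.90/0.95 = 0.947 |
| 0.15 | 0.10 | 0.3 | 0.895/0.93 = 0.962 |
| 0.15 | 0.10 | 0.5 | 0.925/0.95 = 0.974 |
| 0.20 | 0.30 | 0.5 | 0.90/0.85 = 1.059 |
| 0.30 | 0.20 | 2 | 1.30/1.20 = 1.083 |
| 0.20 | 0.20 | any | 1.00 |

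**6. Value of an incomplete chemotherapy record.** Assume equal arms, true chemotherapy use of 40% versus 60%, and a record that captures half of it with no false positives.

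- Recorded use is 20% versus 30%. The propensity score is 0.20/0.50 = 0.40 among recorded users and 0.80/1.50 = 0.533 among the rest.
- Total overlap weight is 0.20 × 0.60 + 0.80 × 0.467 = 0.493 in the first arm, and the same in the second.
- True weighted use is (0.12 + 0.20 × 0.467)/0.493 = 43.2% versus (0.12 + 0.30 × 0.533)/0.493 = 56.8%.
- At 90% capture, the same calculation gives 48.1% versus 51.9%.

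An incomplete term therefore helps somewhat, and better capture helps more.

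**The case against.** The listed terms already do much of the work. A hormonal-only patient scores no on chemotherapy/immunotherapy, radiation and surgery, whereas many newly diagnosed patients score yes on at least one; cancer type and metastasis add to this. The cohort that follows the product label excludes genitourinary cancers, which shrinks the hormonally treated group there. Section 9.9 acknowledges residual confounding. The separate code list cited in Annex 1 might place hormonal agents under an existing item. These points limit how much imbalance is likely. They do not put the two items in the section 9.3.3 list, and a general caveat is no reason to leave out information already derived for eligibility.

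Three stronger readings are tempting and are not supported.

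- A reader might infer that hospital-given chemotherapy will be coded as not used. The protocol does not say so. The sentence on in-hospital medication explains why anticoagulant exposure is taken from GP records. Section 9.4 requests hospital admission data with procedures, and section 9.8 prepares procedure codes. What remains is that no source is named for chemotherapy, so the rule for unrecorded drugs could fall on GP records alone.
- A reader might infer that background cancer treatment as a whole is left unbalanced. Most of it is in the score.
- A reader might infer a bias favouring DOACs of up to two thirds of the detectable effect, from ln(0.925)/ln(0.89) = 0.67. The 0.925 rests on assumed prevalences and an assumed direction. The 0.89 in section 9.5 is for all DOACs versus LMWH, with deaths over the first year. It is not a benchmark for a 3-month rivaroxaban comparison.

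**Conclusion.** The point holds as a specific gap in a fixed adjustment set. Anti-cancer hormonal therapy and recency of diagnosis determine who is eligible but are not propensity score terms, and no later step adjusts for them. Balance on them is not assured, and assurance is weakest in the cancer-subtype analyses.

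Neither the size nor the direction of any bias can be established from the protocol. The assumed scenarios run from 0.925 to 1.083, and the factor is 1.00 if the weighted groups happen to agree. The conclusion rests on two assumptions that the documents make plausible but do not prove: that these factors are prognostic within this cohort, and that they influence the choice of anticoagulant. The change is worth making because it costs almost nothing, not because bias has been shown.

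**What to change.** Add to section 9.3.3, and so to every propensity score model:

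1. anti-cancer hormonal therapy at baseline;
2. time since cancer diagnosis, or the basis for active status: recent diagnosis; chemotherapy, radiotherapy or immunotherapy; hormonal therapy only; metastatic disease. A patient can meet several of these, so use separate indicators or a stated hierarchy. The basis for active status also deals with the difference between the 180-day and 3-month windows.

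Report the weighted balance of these items in each cohort and in each subtype analysis.

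Secondary: state that chemotherapy and radiotherapy are also ascertained from the procedure codes in the hospital admission data already requested, so that the rule treating an unrecorded drug as not used is not applied on GP drug records alone. Keep the GP-recorded chemotherapy term, since even partial capture reduces imbalance.

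The cost is a few extra model terms, built from information already derived for eligibility, and a short change to the protocol wording. In small subtype analyses the number of terms should be watched.
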